4.6.1. Risk Assessment

Potential Risk of Clinical Significance	Summary of Data/Rationale for Risk	Mitigation Strategy
Investigational Product (IP) [UMEC/VI]		
Severe milk protein allergy	Anoro contains Lactose monohydrate (which contains milk protein) as an excipient.	Exclusion criteria have been set for subjects with milk protein allergy.
Cardiovascular effects such as cardiac arrhythmias e.g. supraventricular tachycardia and extrasystoles.	
Class effects associated with LABAs and LAMA containing therapy. The clinical significance of these arrhythmias is unknown. Clinical experience with UMEC/VI to date in completed studies did not show any association with major cardiovascular events.
 
Data available in the product label for UMEC/VI
	
Exclusion criteria have been set for subjects with uncontrolled or severe cardiovascular disease according to the principal investigation's (PI) opinion where the potential risk may outweigh the benefit. The PI should also determine the clinical significance of abnormal ECG findings at screening and exclude subjects who would be at undue risk by participating in the trial. Patients with the following abnormalities will be excluded from participation: atrial fibrillation with rapid ventricular rate >120bpm, sustained or nonsustained ventricular tachycardia, or second degree heart block Mobitz type II or third degree heart block (unless pacemaker or defibrillator had been inserted).

Beta agonists and risk of asthma-related death	Long-acting beta agonists such as vilanterol when used alone may increase the risk of asthma-related death. A placebo-controlled trial with another LABA (salmeterol) showed an increase in asthma-related deaths in subjects receiving salmeterol. This finding with salmeterol is considered a class effect of all LABAs, including vilanterol. Data are not available to determine whether the rate of death in patients with COPD is increased by LABA.	Subjects with a current diagnosis of asthma are excluded from participation in the study.
Paradoxical bronchospasm	As with other inhaled medicines, UMEC/VI can produce paradoxical bronchospasm which may be life threatening.	If paradoxical bronchospasm occurs following dosing with UMEC/VI, this treatment should be discontinued immediately and alternative therapy should be instituted.
Use in patients with narrow-angle glaucoma or urinary retention	No association has been found to date, in completed studies with UMEC/VI or UMEC monotherapy, on glaucoma or urinary retention. However, glaucoma or urinary retention	Exclusion criterion states that subjects with medical conditions such as narrow-angle glaucoma, prostatic hypertrophy, or bladder neck obstruction should only be

Potential Risk of Clinical Significance	Summary of Data/Rationale for Risk	Mitigation Strategy
	have been observed with other antimuscarinic agents, and could potentially be due to the pharmacology.	included if, in the opinion of the principal investigator, the benefit outweighs the risk.
Use of beta blockers	Beta-adrenergic blockers may weaken or antagonize the effect of beta ₂ -agonists such as vilanterol.	The study permitted medications and non drug therapies section states that concomitant administration with beta-blockers is only permitted if, in the Investigator's opinion, the likely benefit outweighs the potential risk.
Pregnancy	There is no experience to date of pregnancy during the use of UMEC/VI.	The study inclusion criteria ensures that female subjects of child bearing potential must have a negative pregnancy test at screening, and agree to a reliable contraceptive method, used consistently and correctly (i.e. in accordance with the approved product label and the instructions of the physician for the duration of the study). Exclusion criteria include Pregnancy : Women who are pregnant or lactating or are planning on becoming pregnant during the study.
Severe hepatic impairment	UMEC/VI has not been studied in severe hepatic impairment.	Exclusion criterion states that subjects severe hepatic impairment should only be included if, in the opinion of the study physician, the benefit outweighs the risk.
Investigational product (IP) [UMEC]		
Cardiovascular effects such as cardiac arrhythmia, e.g. atrial fibrillation and tachycardia	A potential class effect associated with anti-muscarinic therapies. Data available to date in the IB for UMEC [GlaxoSmithKline Document Number RM2006/00835/09	Screening electrocardiogram (ECG) criteria to exclude subjects potentially at risk
Narrow-angle glaucoma, urinary retention	A class effect associated with anti-muscarinic therapies. Data available in the IB for UMEC [GlaxoSmithKline Document Number RM2006/00835/09	Exclusion criterion states that subjects with medical conditions such as narrow-angle glaucoma, prostatic hypertrophy, or bladder neck obstruction should only be included if, in the opinion of the study physician, the benefit outweighs the risk.
Paradoxical bronchospasm that may be life threatening	Known effect associated with inhalation therapy	A short-acting inhaled bronchodilator (albuterol/salbutamol) will be provided for use as needed throughout the study. The investigators will be instructed to assess subject's condition to determine their eligibility to

Potential Risk of Clinical Significance	Summary of Data/Rationale for Risk	Mitigation Strategy
		continue in the study and the need for alternative therapy.
Severe hepatic impairment	UMEC has not been studied in severe hepatic impairment.	Exclusion criterion states that subjects with severe hepatic impairment should only be included if, in the opinion of the study physician, the benefit outweighs the risk.
Pregnancy/Lactation	There is no experience to date of pregnancy during the use of UMEC.	The study inclusion criteria ensure that female subjects enrolled, who are of Child bearing potential, have a negative pregnancy test at screening, and agree to a reliable contraceptive method, used consistently and correctly (i.e. in accordance with the approved product label and the instructions of the physician for the duration of the study). Exclusion criteria states - Pregnancy: Women who are pregnant or lactating or are planning on becoming pregnant during the study.
Study Procedures		
Spirometry procedures	This may cause difficulty breathing, changes in pulse rate and blood pressure, coughing, wheezing, chest tightness or fainting.	Subjects will be monitored during the procedure for these effects and spirometry will be discontinued should these occur.
ECG lead placement	This may cause skin irritation.	It may be necessary to have small patches (about a centimetre in diameter) of hair on the chest shaved to properly attach electrodes to the chest.
Blood sampling procedure (optional pharmacogenetic blood sample)	Giving blood may make subjects feel faint, or experience mild pain, bruising, irritation or redness at the site. In rare cases, they may get an infection	Subjects will be monitored during the blood draw for these effects and should call their study doctor if any of these effects do not resolve
Other		
Side effects of rescue albuterol/salbutamol. Adverse events seen in clinical studies to date are however consistent for the beta ₂ -adrenergic class of compounds	Class effects associated with short acting beta-agonists (SABAs)	Subjects should call their study doctor if they experience any of these symptoms

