4.6. Benefit: Risk Assessment

Summaries of findings from both clinical and non-clinical studies conducted with UMEC/VI and UMEC can be found in the investigator's brochures (IB) [GlaxoSmithKline Document Number [RM2009/00437/07](#)] and [GlaxoSmithKline Document Number [RM2006/00835/09](#)] and in the label information sheets. The current safety profile for UMEC (62.5mcg) and the UMEC/VI (62.5/25mcg) based on data available to date, is comparable with other LABAs and LAMAs. Summary safety data can also be found in the information sheet for salmeterol [[Serevent product information](#), 2003]. The following section outlines the risk assessment and mitigation strategy for this protocol:

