5. SELECTION OF STUDY POPULATION AND WITHDRAWAL CRITERIA

Specific information regarding warnings, precautions, contraindications, adverse events, and other pertinent information on the GSK investigational product or other study treatment that may impact subject eligibility is provided in the IBs, [GlaxoSmithKline Document Number [RM2006/00835/09](#)], [GlaxoSmithKline Document Number [RM2009/00437/07](#)] and product labels.

Deviations from inclusion and exclusion criteria are not allowed because they can potentially jeopardize the scientific integrity of the study, regulatory acceptability or subject safety. Therefore, adherence to the criteria as specified in the protocol is essential.

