5.5. Withdrawal/Stopping Criteria

5.5.1. Withdrawal from the Study

Subjects may be withdrawn from the study at any time by the Investigator if it is considered to be detrimental for them to continue in the study. Reasons for withdrawal from study treatment can include: an AE, clinically significant abnormality, lack of efficacy, sponsor terminated study, pregnancy, or for any other reason.

If a subject withdraws from the study, he/she may request destruction of any samples taken, and the investigator must document this in the site study records.

A reason for the withdrawal from the study must be captured in the electronic case report form (eCRF).

A subject will also be withdrawn from the study, in consultation with the medical monitor and principal investigator, if any of the following stopping criteria are met:

- **Liver Chemistry:** Meets any of the Liver chemistry stopping criteria (See Section [5.5.3](#))

Note: clinical laboratory assessments are not required for this study. However, laboratory samples may be taken for liver event analysis, if clinically indicated by the study investigator.

- **Pregnancy:** Positive pregnancy test (see [Appendix 7](#))

Subjects withdrawn from study treatment will not be replaced.

Note: Withdrawal from study treatment requires withdrawal from the study.

The following actions must be taken in relation to a subject who fails to attend the clinic for a required study visit:

- The site must attempt to contact the subject and re-schedule the missed visit as soon as possible.
- The site must counsel the subject on the importance of maintaining the assigned visit schedule and ascertain whether or not the subject wishes to and/or should continue in the study.

- In cases where the subject is deemed 'lost to follow up', the investigator or designee must make every effort to regain contact with the subject (where possible, 3 telephone calls and if necessary a certified letter to the subject's last known mailing address or local equivalent methods). These contact attempts should be documented in the subject's medical record.
- Should the subject continue to be unreachable, only then will he/she be considered to have withdrawn from the study with a primary reason of "Lost to Follow-up".

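### For paradoxical bronchospasm, Section 4.6.1 says stop on UMEC/VI but assess whether to continue on UMEC, and gives blinded sites no rule that works without knowing the arm

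*Protocol*

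**What the plan says.** Section 4.6 introduces the risk table as trial strategy: "The following section outlines the risk assessment and mitigation strategy for this protocol". The table has a block for UMEC/VI and a block for UMEC, and paradoxical bronchospasm appears in both.

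- **UMEC/VI block.** The risk is stated as "UMEC/VI can produce paradoxical bronchospasm which may be life threatening". The action is: "If paradoxical bronchospasm occurs following dosing with UMEC/VI, this treatment should be discontinued immediately and alternative therapy should be instituted".
- **UMEC block.** The risk is stated as "Paradoxical bronchospasm that may be life threatening". Rescue albuterol/salbutamol is supplied, and the action reads "The investigators will be instructed to assess subject's condition to determine their eligibility to" and, after the page break, "continue in the study and the need for alternative therapy".

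There is no salmeterol block for any risk.

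The related provisions are these:

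- **Section 5.5.1** lets the investigator withdraw a subject for whom continuing would be detrimental, and names an adverse event as a possible reason. It also requires withdrawal, "in consultation with the medical monitor and principal investigator, if any of the following stopping criteria are met"; the criteria that follow are liver chemistry and pregnancy. Stopping study treatment means leaving the study.
- **Section 6.3** gives every subject both an ELLIPTA and a DISKUS inhaler.
- **Section 6.5** sets the double blind. It allows unblinding in an emergency, or for a serious condition where knowing the treatment is essential to care. A subject unblinded by the investigator or treating physician is withdrawn.

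**The concern.** The instruction for a possibly life-threatening event depends on an assignment the site cannot see. What the investigator observes is bronchospasm after a blinded inhalation, not bronchospasm after UMEC/VI or after UMEC. One row directs a stop and the other leaves continuation open, so the same presentation can end in a stop at one site and continued dosing at another. Continued dosing would go against the UMEC/VI instruction whenever the subject is in that arm. At stake are subject safety and uniform conduct across roughly 205 sites, not the test of the primary hypothesis.

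**Working it through.** This is mainly a comparison of text.

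**1. Do the actions differ?** Yes. The UMEC/VI row directs immediate discontinuation. The UMEC row asks for an assessment that may end in continuation. The same two rows stand in the original protocol and in the amended text.

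**2. Does the protocol give a reason for the difference?** No. Each row attributes the event to inhaled therapy in general. That reasoning would cover salmeterol as well, which the table omits.

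**3. Can the rows be applied by arm?** Not under the blind. The inhaler regimen looks the same in all three arms (Section 6.3), so the inhaler that preceded the event does not reveal the assignment.

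**4. What happens to the continue option in the UMEC row?**

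| Site's choice | Consequence |
|---|---|
| Unblind to confirm UMEC | The subject must be withdrawn (Section 6.5), so continuing is no longer possible |
| Stay blinded and continue | UMEC/VI cannot be excluded, so the UMEC/VI row may be breached |
| Stay blinded and stop | Both rows are satisfied |

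The continue option can therefore never be used with assured compliance. Stopping is the only action that is always safe under both rows, and the protocol does not say so.

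**5. Does another section supply a default?** None was found in the text available. The mandatory criteria in Section 5.5.1 do not include the event. The discretionary withdrawal clause and emergency unblinding are permissive. Section 12.4.2 mentions allergic bronchospasm only as an example of a serious event.

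**6. The one figure the protocol supports.** Section 9.2 gives about 808 subjects per arm and the synopsis gives 2424 randomised. If the event is equally likely in each arm (an assumption):

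P(on UMEC/VI | blinded event) = 808 / 2424 = 0.333, or 1/3.

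This only restates the allocation ratio; it does not measure harm. With no event rate in the protocol, no count of affected subjects, withdrawals or power loss can be derived.

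**The case against.** The strongest reply is that nothing here is contradictory. Each row sits under its own product heading, and the UMEC row does not tell anyone to continue. An investigator who cannot rule out UMEC/VI meets both rows by stopping. Arm-independent handling also exists: discretionary withdrawal (Sections 5.5.1 and 5.5.2), emergency unblinding without first contacting the sponsor (Section 6.5), and 24-hour reporting of serious events (Section 7.4.1.1), after which sponsor safety staff may unblind. The UMEC row says investigators will be instructed, which suggests guidance elsewhere. Section 5 also sends sites to the investigator's brochures and product labels for "Specific information regarding warnings, precautions, contraindications, adverse events, and other pertinent information on the GSK investigational product or other study treatment", and those are not available here.

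Much of this stands, and it is why the point is minor. It narrows the problem to an event that is judged not to need emergency unblinding and that an investigator might consider safe to dose through. It does not remove the problem, because none of these provisions sets a default for that case. Product-specific brochures and labels would raise the same difficulty of not knowing the product.

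There is also an objection to the remedy: it turns a clinical assessment into mandatory withdrawal in all arms, without defining how paradoxical bronchospasm is told apart from COPD worsening or wheeze after spirometry. The trade-off is real. The diagnosis, however, is already required by the UMEC/VI row, so the rule asks for no new judgement.

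**Conclusion.** The point holds, as a minor one. The protocol ties the action for a possibly life-threatening event to a blinded assignment and states no arm-independent default. The rows can be reconciled by stopping, but a site has to work that out for itself, and the UMEC row suggests that continuing is acceptable.

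The size cannot be put beyond the 1/3 chance of UMEC/VI assignment, which rests on equal event risk across arms. The primary endpoint analysis and its alpha are not affected.

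The conclusion is limited to the protocol text available, which includes the bodies of both the original and the amended versions. It makes no claim about what the brochures, labels or site instructions say.

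**What to change.** Replace the two bronchospasm rows in Section 4.6.1 with one rule for every arm: *if paradoxical bronchospasm follows any blinded ELLIPTA or DISKUS inhalation, stop blinded study treatment immediately and start alternative therapy; unblind only under the conditions in Section 6.5.*

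Add the event to the stopping criteria in Section 5.5.1, with a line saying that *treatment stops at once, and consultation with the medical monitor follows and must not delay the stop.* That line is needed because the criteria there are introduced as applied in consultation. The liver criterion shows that the two can coexist: it is listed under the same consultation wording, while Appendix 2 calls for an immediate stop. It is an imperfect precedent, since Appendix 2 also allows the subject to remain in the study for follow-up while Section 5.5.1 requires withdrawal. The fix does not depend on it.

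The cost is a wording change in Section 4.6.1 and one bullet in Section 5.5.1. No new procedure, data field or withdrawal code is needed, because the adverse event reason in Section 5.5.2 already covers it. The downside is that a few subjects on UMEC or salmeterol who might have continued would leave the study; the protocol gives no basis for estimating how many.

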4.6.2. Benefit Assessment

Subjects will receive single or combination of long-acting bronchodilator therapies approved for maintenance treatment of COPD. Participating subjects in this study will contribute to the process of further characterizing the benefit of these long-acting bronchodilators with respect to PROs and symptoms in the treatment of COPD.

Specific benefits associated with the study design and procedures include the following:

- Subjects will receive treatments approved for the treatment of COPD that have been shown to be effective in the population under study
- All subjects will receive albuterol/salbutamol for use “as needed” for relief of COPD symptoms
- The combination of study procedures of spirometry, CAT, SGRQ, TDI, E-RS will provide the study subjects with a comprehensive evaluation of their symptoms, health status and COPD disease severity. Subjects will also be monitored throughout the study for any worsening of COPD symptoms or decline in general health. Finally smoking cessation counselling will also be provided.

4.6.3. Overall Benefit: Risk Conclusion

Taking into account the measures taken to minimize risk to subjects participating in this study, the potential risks identified in association with UMEC/VI, UMEC, salmeterol and with study procedures are justified by the anticipated benefits from active treatments that may be afforded to patients with COPD.

5. SELECTION OF STUDY POPULATION AND WITHDRAWAL CRITERIA

Specific information regarding warnings, precautions, contraindications, adverse events, and other pertinent information on the GSK investigational product or other study treatment that may impact subject eligibility is provided in the IBs, [GlaxoSmithKline Document Number [RM2006/00835/09](#)], [GlaxoSmithKline Document Number [RM2009/00437/07](#)] and product labels.

Deviations from inclusion and exclusion criteria are not allowed because they can potentially jeopardize the scientific integrity of the study, regulatory acceptability or subject safety. Therefore, adherence to the criteria as specified in the protocol is essential.

5.1. Inclusion Criteria

A subject will be eligible for inclusion in this study only if all of the following criteria apply:

AGE
1. 40 years or older at date of signing informed consent at Screening Visit 1

TYPE OF SUBJECT AND DIAGNOSIS INCLUDING DISEASE SEVERITY	
2.	Outpatient with a diagnosis of COPD in accordance with the definition of the American Thoracic Society/European Respiratory Society (ATS/ERS) [Celli , 2004].
3.	FEV₁ : Persistent airflow limitations as indicated by: A pre and post-albuterol/salbutamol FEV ₁ /FVC ratio of <0.70 and a post-albuterol/salbutamol FEV ₁ of $\geq 30\%$ to $\leq 80\%$ predicted normal values at Screening Visit 1. Predicted values will be based upon the ERS Global Lung Function Initiative [Quanjer , 2012].
4.	CAT score : A CAT score of ≥ 10 at Screening Visit 1

Smoking History	
5.	Current or former cigarette smokers with a history of cigarette smoking of ≥ 10 pack-years [number of pack years = (number of cigarettes per day / 20) x number of years smoked (e.g. 20 cigarettes per day for 10 years, or 10 cigarettes per day for 20 years both equal 10 pack-years)]. Former smokers are defined as those who have stopped smoking for at least 6 months prior to Visit 1. Pipe and/or cigar use cannot be used to calculate pack-year history.

SEX	
6.	
Male and female subjects are eligible to participate in the study
 
A female subject is eligible to participate if she is not pregnant (as confirmed by a negative urine human chorionic gonadotrophin (hCG) test), not lactating, and at least one of the following conditions applies:
 
a. Non-reproductive potential defined as:
 
Pre-menopausal females with one of the following:
 
 • Documented tubal ligation • Documented hysteroscopic tubal occlusion procedure with follow-up confirmation of bilateral tubal occlusion • Hysterectomy • Documented Bilateral Oophorectomy 
Postmenopausal defined as 12 months of spontaneous amenorrhea. In questionable cases a blood sample with simultaneous follicle stimulating hormone (FSH) and estradiol levels consistent with menopause must be tested. Females on hormone replacement therapy (HRT) and whose menopausal status is in doubt will be required to use one of the highly effective contraception methods if they wish to continue their HRT during the study. Otherwise, they must discontinue HRT to allow confirmation of post-menopausal status prior to study enrolment.
 
b. Reproductive potential and agrees to follow one of the options listed in the Modified List of Highly Effective Methods for Avoiding Pregnancy in Females of

Reproductive Potential (FRP) ([Appendix 7](#)) from 30 days prior to the first dose of study medication and until [at least five terminal half-lives OR until any continuing pharmacologic effect has ended, whichever is longer] after the last dose of study medication and completion of the follow-up visit.

The investigator is responsible for ensuring that subjects understand how to properly use these methods of contraception.

INFORMED CONSENT

7. **Capable of giving signed informed consent** prior to study participation, which includes compliance with the requirements and restrictions listed in the consent form and in this protocol.

